8.7 ECG Examination

ECG examination will be assessed at screening and 24 hours (± 2 hours) after study medication administration.

Number of subjects with abnormal results will also be summarized by treatment and time point. All ECG data will be listed.

8.8 Clinical Laboratory Evaluation

Clinical laboratory tests (blood chemistry, hematology and urinalysis) will be collected at screening and before discharge from the inpatient unit (T96h). All results will be listed. For each individual lab test value, the raw value and change from screening will be summarized by treatment.

Each clinical laboratory test will be defined by the clinical laboratory to be “Low”, “Normal”, or “High”, according to the normal reference range from the clinical laboratory. The number and percentage of subjects who have a shift from within to outside the normal reference range from screening to T96h will be summarized by treatment.

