#### **15.7.2. Clinical Laboratory Evaluations**

For continuous laboratory parameters, descriptive statistics will be presented for the value at each assessment time and for the changes from baseline screening labs by treatment group.

Additionally, clinical laboratory parameters will be categorized as low, normal, or high according to laboratory range specifications and the number and percentage of subjects in each category will be presented in shift tables.

Laboratory values that are outside the normal range will also be flagged in the data listings, along with corresponding normal ranges.

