Table 14.3.1.5	Safety Population	Summary of TEAEs Leading to Discontinuation from Study
Table 14.3.1.6	Safety Population	Summary of TEAEs by System Organ Class, Preferred Term and Severity
Table 14.3.1.7	Safety Population	Summary of TEAEs by System Organ Class, Preferred Term and Relationship to Study Drug
Table 14.3.2.1.1	Safety Population	Summary of Blood Chemistry Laboratory Tests: Results and Change from Baseline
Table 14.3.2.1.2	Safety Population	Summary of Blood Chemistry Laboratory Tests: Shifts from Baseline
Table 14.3.2.2.1	Safety Population	Summary of Hematology Laboratory Tests: Results and Change from Baseline
Table 14.3.2.2.2	Safety Population	Summary of Hematology Laboratory Tests: Shifts from Baseline
Table 14.3.2.3.1	Safety Population	Summary of Urinalysis Laboratory Tests: Results and Change from Baseline
Table 14.3.2.3.2	Safety Population	Summary of Urinalysis Laboratory Tests: Shifts from Baseline
Table 14.3.4	Safety Population	Summary of Vital Signs: Results and Change from Baseline
Table 14.3.5	Safety Population	Summary of Surgical Site Assessment
Table 14.3.6.1	Safety Population	Summary of Neurosensory Exam –Target Foot
Table 14.3.6.2	Safety Population	Summary of Neurosensory Exam –Non-Target Foot
Table 14.3.7	Safety Population	Summary of ECG Exam Abnormal Findings

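### SAP 8.8 narrows the protocol's low/normal/high laboratory shift tables to one within-to-outside count, which does not separate direction and omits subjects already out of range at screening

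*SAP*

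**What the plan says.** Protocol 15.7.2 states that "clinical laboratory parameters will be categorized as low, normal, or high according to laboratory range specifications" and that "the number and percentage of subjects in each category will be presented in shift tables".

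SAP 8.8 starts from the same classification: "Each clinical laboratory test will be defined by the clinical laboratory to be “Low”, “Normal”, or “High", using the laboratory's reference range. The shift summary that follows is "The number and percentage of subjects who have a shift from within to outside the normal reference range from screening to T96h", by treatment. SAP 8.8 also says that all results will be listed and that "the raw value and change from screening will be summarized by treatment".

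SAP 14.1.1 plans three shift tables: "Summary of Blood Chemistry Laboratory Tests: Shifts from Baseline" (Table 14.3.2.1.2), "Summary of Hematology Laboratory Tests: Shifts from Baseline" (Table 14.3.2.2.2) and "Summary of Urinalysis Laboratory Tests: Shifts from Baseline" (Table 14.3.2.3.2). These are titles without a layout.

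SAP 12, the section for changes to the protocol's analyses, lists none. It only defers any deviations to the clinical study report.

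**The concern.** The two texts are both current and do not describe the same display. A programmer who builds the shift tables from SAP 8.8 would produce one count and one percentage per test and arm, because 8.8 is the only text that defines their content.

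Two kinds of information would be lost.

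- **Direction.** A fall and a rise out of range are different findings for tests such as sodium, potassium, glucose and calcium. Protocol Appendix H grades the low and high directions of these four separately.
- **Subjects abnormal at screening.** Exclusion criterion 3 in protocol 10.2 bars only clinically significant laboratory abnormalities that could impair participation or interfere with assessments. Other out-of-range values can be enrolled, and ASA class 3 subjects and subjects on stable diabetic regimens are eligible. A subject with high glucose at screening and low glucose at T96h would not appear in the count for glucose.

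Laboratory results are a named safety endpoint, and T96h is the only scheduled post-dose draw. With about 36 subjects per arm and no formal safety testing, simple per-subject counts are a natural way to look for a dose-related pattern.

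**Working it through.** The plan states no figure on this point, so there is none to reproduce. The check is a comparison of wording plus simple arithmetic.

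**Step 1. Which cells does the SAP sentence count?** Cross the three screening categories with the three T96h categories:

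| Screening | T96h Low | T96h Normal | T96h High |
|---|---|---|---|
| Low | not reported | not reported | not reported |
| Normal | counted | not reported | counted |
| High | not reported | not reported | not reported |

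- Cells in the full table: 3 × 3 = 9.
- Cells that the SAP sentence counts: 2 (Normal-to-Low and Normal-to-High), reported as 1 number.
- Changes of category: 9 − 3 on the diagonal = 6. Omitted: 6 − 2 = 4 (Low-to-Normal, Low-to-High, High-to-Normal, High-to-Low).
- Cells with an abnormal screening value: 2 rows × 3 = 6, none reported.

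**Step 2. What does the missing direction do?** Take assumed counts with 36 subjects per arm (SAP 2.2.4). One arm has 6 subjects moving Normal-to-High and none Normal-to-Low. Another has 6 moving Normal-to-Low and none Normal-to-High. With all 36 as denominator, both arms report 6/36 = 16.7%. A low/normal/high table would show 6 against 0 in each direction.

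**Step 3. How many subjects cannot enter the count for a given test?** Expected number per arm = 36 × q, where q is the proportion out of range on that test at screening. The documents do not give q, so a range is shown:

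| Assumed q | Per arm of 36 |
|---|---|
| 2% | 0.7 |
| 5% | 1.8 |
| 10% | 3.6 |
| 20% | 7.2 |

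This applies test by test. A subject out of range on one test can still be counted on every other test.

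**Step 4. Does another part of the SAP restore the protocol's table?** SAP 3 has a general policy of summarizing categorical assessments by treatment and time point. Even if it applies here, it gives separate frequencies at screening and at T96h, not transitions. Beyond the shift tables, the laboratory tables listed in SAP 14.1.1 are titled as results and change from baseline, and none is titled as a frequency table of the three categories. The shift-table titles would fit a full layout but do not specify one.

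**The case against.** The strongest case on the other side has five parts.

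- **Other by-arm counts exist.** A reader might infer that the shift table is the only planned count of subjects with abnormal laboratory values. The documents do not support that. Protocol 12.5.1 makes specified elevations of ALT, AST, bilirubin and alkaline phosphatase, and any other change the investigator judges clinically significant, an adverse event. SAP 8.2 counts treatment-emergent events by arm, system organ class and preferred term. This stands and limits the impact. That route depends on thresholds or judgment, so it does not replace a range-based count.
- **Pooling is not stated.** SAP 8.8 never says that low and high are combined, and assigning three labels suggests that direction may have been intended. This stands in part: pooling is the plain reading of the sentence, not an explicit rule. The ambiguity is itself a reason to rewrite it.
- **No denominator is given.** A reader might infer that subjects abnormal at screening stay in the percentage as stable. SAP 8.8 does not say so. The denominator could be all subjects, those with both values, or those normal at screening.
- **Other laboratory summaries remain.** Raw values and change from screening by arm, with minimum and maximum, would tend to show opposite movements such as those in the assumed example. They do not give per-subject counts by direction, but the information is not lost. They also show worsening within a category, which a low/normal/high table does not.
- **The SAP may settle presentation.** Protocol 15.1 leaves it to the SAP to say how data are presented. That is fair, but SAP 12 records no choice to depart from the display that protocol 15.7.2 names.

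**Conclusion.** The point holds as a discrepancy of modest weight. On its plain wording, SAP 8.8 specifies a less informative laboratory shift summary than protocol 15.7.2, and the change is not declared. The size depends on the rate of out-of-range screening values, for which 5% to 10% per test is an assumption.

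It would be tempting to multiply over all the laboratory tests and quote the share of subjects out of range on at least one. That share describes no planned table, because shifts are tabulated per test, and it would need independence among tests that are plainly related, such as hemoglobin and hematocrit.

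No efficacy result or confirmatory conclusion is affected.

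**What to change.** In SAP 8.8, replace the within-to-outside sentence with this rule: for each test and treatment group, present a shift table of Low/Normal/High at screening by Low/Normal/High at T96h, with n and % of subjects having both values. Show it in Table 14.3.2.1.2 (chemistry) and Table 14.3.2.2.2 (hematology), and in Table 14.3.2.3.2 for urinalysis items that have a reference range. The both-values denominator is an addition, because neither document states one.

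If the sponsor prefers the narrower count, SAP 12 should record and justify the departure, and 8.8 should state the denominator and whether low and high are shown separately.

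The cost is one sentence and slightly longer tables. The flags are already assigned under 8.8, so no new data or subjects are needed.

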8.9 Drugs of Abuse and Alcohol Screens, Pregnancy Test

Pregnancy (for female subjects of childbearing potential), urine drug screen and alcohol (breath or saliva) tests will be performed at screening and pre-surgery.

Results will be listed for individual subjects. Each test result will be defined to be “negative” or “positive”.

8.10 Subject Pain Assessment Training and Surgery Details

Patient pain assessment training and surgery details will be documented in CRFs and will be listed for each subject.

9 PHARMACOKINETIC EVALUATION

It is anticipated that approximately 1/3rd of enrolled subjects at each site will participate in the PK study (48 in total; 12 in each treatment group).

Blood draws for PK samples will be collected at baseline (within the 30 minutes before the start of study treatment dosing), and at minutes 5, 10, 15, 30, 45, hours 1, 1.5, 2, 2.5, 3, 4, 6, 8, 12, 16, and 24 (a total of 17 samples). Actual sampling times will be used to calculate following plasma bupivacaine-derived PK parameters using noncompartmental analysis for CA-008, capsaicin and CA-101:

- C_{max} : The maximum measured plasma concentration, obtained directly from the data without interpolation
- C_{last} : Last observed (quantifiable) concentration
- T_{max} : Time of C_{max}
- $t_{1/2}$: The apparent first-order terminal elimination half-life, calculated as $0.693/\lambda_z$
- T_{lag} : Time delay between drug administration and first measurable (above lower limit of quantitation) concentration
- T_{last} : Time of occurrence of C_{last}
- λ_z : Terminal first-order elimination rate constant
- AUC_{0-t} : Area under the plasma concentration-time curve from time 0 to the last measurable concentration (where time is post dose), calculated by the linear trapezoidal method
- $AUC_{0-\infty}$: Area under the plasma concentration-time curve, from time of dosing to infinity.
- AUC_{last} : Area under the plasma concentration-time curve, from time of dosing to the time of the last measurable concentration

Sponsor: Concentric Analgesics, Inc.
Protocol Number: CA-PS-201

Statistical Analysis Plan
Date: 09OCT2018

PK concentration data will be listed. There will be a separate PK Analysis Plan that will describe PK analyses.

10 OTHER ANALYSES

Any additional analyses not included in this SAP conducted after database lock will be considered exploratory and identified as Post Hoc in the CSR.

11 INTERIM ANALYSES

There are no planned interim analyses for this study.

12 CHANGES TO THE ANALYSES PLANNED IN THE PROTOCOL

Any deviations from the statistical plan will be described and a justification given in the CSR.

Table 14.2.2.5.1	mITT Population	Summary of NRS at Rest and with Walking by Time Point (WOCF)
Table 14.2.2.5.2	mITT Population	Summary of NRS at Rest and with Walking by Time Point and by Site (WOCF)

Table 14.2.2.6	mITT Population	Summary of NRS at Rest and with Walking by Time Point (LOCF)
Table 14.2.2.7.1	mITT Population	Summary of NRS at Rest and with Walking by Time Point (Observed Data, No Imputation for Drop Out)
Table 14.2.2.7.2	mITT Population	Summary of NRS at Rest and with Walking by Time Point and by Site (Observed Data, No Imputation for Drop Out)
Table 14.2.3	mITT Population	Logistic Analysis of Proportion of Subjects who are Opioid Free Outcome (Key Secondary and Exploratory Analyses)
Table 14.2.4.1.1	mITT Population	ANOVA Analysis of Opioid Consumption (in Morphine equivalents) (Key Secondary and Exploratory Analyses)
Table 14.2.4.1.2	mITT Population	ANOVA Analysis of Opioid Consumption by Site (in Morphine equivalents) (Key Secondary and Exploratory Analyses)
Table 14.2.4.2.1	mITT Population – Subjects Who Took Any Opioid Medication	ANOVA Analysis Mean Daily Opioid Consumption (in Morphine Equivalents)
Table 14.2.4.2.2	mITT Population – Subjects Who Took Any Opioid Medication	ANOVA Analysis Mean Daily Opioid Consumption by Site (in Morphine Equivalents)
Table 14.2.5.1	Safety Population	Kaplan-Meier Analysis of Time to First Use of Opioid Rescue Medication
Table 14.2.5.2	Safety Population – Subjects Who Took First Opioid Rescue Medication Prior to 60 Minutes Post-Dose	Kaplan-Meier Analysis of Time to Second Use of Opioid Rescue Medication
Table 14.2.6	mITT Population	CMH and Fishers Analysis of Patient Global Evaluation (PGE)
Table 14.2.7	mITT Population	CMH and Fishers Analysis of Investigator Global Evaluation (IGE)
Table 14.2.8	mITT Population	Fishers Analysis of Proportion of Drop Out During the Inpatient Period
Table 14.2.9.1	Safety Population	Fishers Analysis of Percent of Subjects using Rescue Medication Over Time
Table 14.2.9.2	Safety Population	Summary of Percent of Subjects Using Rescue Medication by Day
Table 14.3.1.1	Safety Population	Overall Summary of Treatment-Emergent Adverse Events (TEAEs)
Table 14.3.1.2	Safety Population	Summary of TEAEs by System Organ Class and Preferred Term

Table 14.3.1.3	Safety Population	Summary of Treatment Related TEAEs by System Organ Class and Preferred Term
Table 14.3.1.4	Safety Population	Summary of SAEs by System Organ Class and Preferred Term
Table 14.3.1.5	Safety Population	Summary of TEAEs Leading to Discontinuation from Study
Table 14.3.1.6	Safety Population	Summary of TEAEs by System Organ Class, Preferred Term and Severity
Table 14.3.1.7	Safety Population	Summary of TEAEs by System Organ Class, Preferred Term and Relationship to Study Drug
Table 14.3.2.1.1	Safety Population	Summary of Blood Chemistry Laboratory Tests: Results and Change from Baseline
Table 14.3.2.1.2	Safety Population	Summary of Blood Chemistry Laboratory Tests: Shifts from Baseline
Table 14.3.2.2.1	Safety Population	Summary of Hematology Laboratory Tests: Results and Change from Baseline
Table 14.3.2.2.2	Safety Population	Summary of Hematology Laboratory Tests: Shifts from Baseline
Table 14.3.2.3.1	Safety Population	Summary of Urinalysis Laboratory Tests: Results and Change from Baseline
Table 14.3.2.3.2	Safety Population	Summary of Urinalysis Laboratory Tests: Shifts from Baseline
Table 14.3.4	Safety Population	Summary of Vital Signs: Results and Change from Baseline
Table 14.3.5	Safety Population	Summary of Surgical Site Assessment
Table 14.3.6.1	Safety Population	Summary of Neurosensory Exam –Target Foot
Table 14.3.6.2	Safety Population	Summary of Neurosensory Exam –Non-Target Foot
Table 14.3.7	Safety Population	Summary of ECG Exam Abnormal Findings

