## 15.6. Analysis of Efficacy Measures

All efficacy endpoints (e.g., NRS scores), will be summarized over time by treatment using descriptive statistics including confidence intervals as appropriate.

AUC calculations will be done using the standard trapezoidal rule

$$AUC = \sum_{i=0}^x \left( \frac{NRS_i + NRS_{i+1}}{2} \right) * (T_{i+1} - T_i)$$

Where:  $NRS_i$  = NRS at time  $i$ , and  $(T_{i+1} - T_i)$  is the Time difference in minutes between time  $i$  and time  $i+1$ . A similar calculation and handling of missing data will be performed for the NRS scores with ambulation.

In this study, subjects are permitted to take rescue medication for analgesia. It is expected subjects randomized to placebo arm will take rescue medication more often. During both inpatient and outpatient portions of the study, the subjects will be instructed to record NRS immediately prior (within approximately 15 min) to taking rescue medication.

Missing NRS will be handled as discussed in the Study's SAP and as briefly outlined in [Section 15.6.4](#).

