7.5.4 Total Opioid Consumption (in Daily Oral Morphine Equivalents)

The amount of opioids taken as rescue will be calculated using the rescue medication page of the eCRF. If additional opioids, other than the study rescue medications, appear on the concomitant medications page and can be identified, those opioids will also be included (in terms of morphine equivalents) in the total consumed. [Table 7-1](#) will be used to calculate the morphine equivalent dose (MED) for each medication. The total opioid consumption for each day for each subject will be calculated as the sum of the MEDs of all of the medications taken on that day. For example, if a subject takes 5 MED morphine on Day 1 and Day 2, and 10 MED of Oxycodone on Day 2, the total consumption for Day 1 is 5 MED, and the total consumption for Day 2 is 15 MED. Subjects that take no opioids on a day will have a total opioid consumption value of zero for that day.

Table 7-1 Table of Equianalgesic Conversion

Opioid (Doses in mg)	Conversion Factor
Hydrocodone	1
Hydromorphone	4
Morphine	1
Oxycodone	1.5
Tramadol	0.1
Multiply the opioid dose by the conversion factor = morphine equivalent dose (MED): e.g., oxycodone 5 mgX1.5 = 7.5 mg MED	

Total opioid consumption will be calculated overall and for the same periods as the NRS AUC values: 0-96 hours ($OC_{0 \text{ to } 96h}$), 24-48 hours ($OC_{24 \text{ to } 48h}$), 24-72 hours ($OC_{24 \text{ to } 72h}$) and 24-96 hours ($OC_{24 \text{ to } 96h}$). In addition, analgesic consumption (AC) from T96h to W1 ($AC_{96h \text{ to } W1}$) and AC_{96h} to W2 will also be summarized. An ANOVA with treatment arm as the main effect will be performed and the same types of comparisons as described in Section 7.4.1 will be presented. A separate summary containing only subjects that have taken at least one dose of rescue will be performed if warranted.

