7.5.5 Time to First Use of Rescue Medication

For the analysis of time to use of rescue medication, only OPIOID rescue medication will be included,

The time to first rescue will be measured from Time 0 (time of completion of study drug administration) and 24 hours post-dose. If a subject does not take rescue medication but prematurely discontinues from the study, then for analysis purposes the subject's observation time will be the time of the discontinuation. The observation time will be considered to be a rescue event if the discontinuation was due to LOE, otherwise, it will be considered a censored observation.

The distributions of time to first rescue in each treatment group will be presented graphically using Kaplan-Meier plots.

If data warrant, a summary table will present the number of subjects receiving rescue medication, number of censored subjects, median time to first dose of rescue, and 95% confidence intervals of the medians by treatment groups. Individual times to event will be listed. Subjects will be followed at the time of discontinuation if no rescue medication was received prior to discontinuation. For the time to first rescue medication after 24 hours post-dose, subjects will be censored at 24 hours if the subject drop out the study prior to Hour 24.

Time to second rescue will also be explored for subjects who receive the first rescue prior to 60 minutes post-dose. Subjects will be censored at the time of discontinuation if the subject receives only 1 rescue medication. The observation time will be considered to be a rescue event if the discontinuation was due to LOE, otherwise, it will be considered a censored observation

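### SAP Tables 14.2.4.2.1 and 14.2.4.2.2 plan a between-arm ANOVA of opioid dose among opioid users only, a post-randomisation subset that SAP 7.5.4 proposes merely to summarise

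*SAP*

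**What the plan says.** SAP 7.5.4 sets out the opioid-consumption analysis. Doses are converted to morphine equivalents (MED) and totalled per subject per day. Non-users stay in: "Subjects that take no opioids on a day will have a total opioid consumption value of zero for that day". For the comparison, "An ANOVA with treatment arm as the main effect will be performed". The corresponding table, 14.2.4.1.1, is in the full mITT population and is titled "ANOVA Analysis of Opioid Consumption (in Morphine equivalents) (Key Secondary and Exploratory Analyses)".

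For users alone, SAP 7.5.4 has one sentence: "A separate summary containing only subjects that have taken at least one dose of rescue will be performed if warranted". It names no method.

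The table list in SAP 14.1.1 goes further. Tables 14.2.4.2.1 and 14.2.4.2.2 restrict mITT to "Subjects Who Took Any Opioid Medication" and are titled "ANOVA Analysis Mean Daily Opioid Consumption (in Morphine Equivalents)", the second by site. They are listed without condition and carry neither a key secondary nor an exploratory label. SAP 7.3 puts every efficacy analysis outside the hierarchy at two-sided 0.05 without adjustment.

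Protocol 15.6 says of rescue: "It is expected subjects randomized to placebo arm will take rescue medication more often". SAP 7.4.2 ranks opioid-free status from 0 to 96 h first among the key secondary endpoints.

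**The concern.** Membership of the users-only subset is an outcome. If CA-008 makes some low-need subjects opioid-free, they leave the active arm's denominator while their counterparts remain in the placebo arm's. The two groups of users are then no longer comparable by randomisation, and the ANOVA mixes the drug's effect on dose with its effect on who takes any dose. The more the drug succeeds on the first key secondary endpoint, the larger this distortion can be.

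At stake is a reported difference, with a p-value, that a reader could take as evidence about opioid sparing. There is also a conflict for the programmer: a conditional summary in the body, an unconditional ANOVA in the table list. The body defines the subset by rescue, the tables by opioid medication, and neither states the time window that makes someone a user.

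**Working it through.** The plan gives no figure for the users-only analysis and no distribution of opioid use, so there is nothing of its own to reproduce on this point. The following come from the documents: 36 subjects per arm (SAP 2.2.4); 7.5 mg MED per 5 mg oxycodone dose (SAP Table 7-1); and rescue intervals that allow about 12/2 + 84/4 = 6 + 21 = 27 doses in 96 h (Protocol 9.1.3). The pattern of use is assumed throughout.

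**1. Fixed example, 36 per arm, 4 days.** Assume that under placebo 4 subjects take nothing, 12 take 2 doses and 20 take 14 doses. The drug spares 2 doses in every user, so no one takes more on active than on placebo. One dose over four days is 7.5/4 = 1.875 mg MED/day.
- Total doses: placebo 12×2 + 20×14 = 304; active 20×12 = 240.
- Full mITT with zeros: 304×1.875/36 = 15.83 against 240×1.875/36 = 12.50; difference **-3.33**.
- Users only: 304×1.875/32 = 17.81 against 240×1.875/20 = 22.50; difference **+4.69**.

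Two variations show what drives this:
- If only 1 dose is spared, nobody becomes opioid-free. Users-only is 15.94 - 17.81 = -1.87 and full mITT is 14.17 - 15.83 = -1.66, so there is no distortion of sign.
- If the light users take 4 doses and 4 are spared, users-only is 18.75 - 19.22 = -0.47 against 10.42 - 17.08 = -6.66 in full mITT. The sign is right but most of the effect is lost.

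**2. Two continuous illustrations (mg MED, 0 to 96 h).**
- Placebo use is gamma with shape 1.5 and scale 30 (mean 45). The drug abolishes use in those who would need under 25 mg and changes no one else. P(use) on active is 0.644 and the active mean with zeros is 40.19. All subjects: 40.19 - 45 = **-4.8**. Users only: 40.19/0.644 - 45 = **+17.4**. With cut-offs of 7.5, 15 and 40 mg, users-only is +3.6, +9.1 and +30.8 against -0.4, -1.7 and -11.2.
- Latent need is normal with SD 30, its mean shifts from 40 to 20, and use is zero when need is negative. P(use) is 0.91 against 0.75. All subjects: 24.53 - 41.27 = **-16.7**. Users only: 32.82 - 45.41 = **-12.6**, which is 75% of the full difference.

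**3. Simulation.** There were 4,000 trials per row, 36 per arm, with a two-arm t-test standing in for the four-arm ANOVA. Placebo has 10% non-users, a stated share of light users (mean 2 doses), and the rest heavy users (mean 14 doses, capped at 27). Differences are in mg MED/day.

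| Light users | Made opioid-free | Cut in heavy users' doses | Full mITT | Users only | Users-only worse on active | Significantly worse |
|---|---|---|---|---|---|---|
| 40% | 90% | 0% | -1.3 | +8.2 | 99.8% | 71% |
| 40% | 90% | 10% | -2.7 | +5.7 | 97.3% | 43% |
| 40% | 90% | 20% | -3.9 | +3.3 | 88.6% | 17% |
| 40% | 90% | 50% | -7.8 | -3.9 | 6% | 0% |
| 20% | 90% | 10% | -2.4 | +1.8 | 77% | 8% |
| 60% | 90% | 10% | -2.7 | +8.7 | 99.5% | 65% |
| 40% | 50% | 10% | -2.0 | +1.7 | 72% | 8% |
| 0% | not applicable | 30% | -7.1 | -7.9 | 0% | 0% |

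The full-mITT test was significantly in the wrong direction in under 1% of trials in every row.

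**The case against.** The strongest reply is that these are supportive tables. The population column states the restriction openly, opioid-free status is reported separately in Table 14.2.3, and nothing in the testing hierarchy depends on the users-only result. All of that stands, and it limits the severity.

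Three stronger readings are tempting, and the documents do not support them.
- *That the opioid-sparing result itself is compromised.* It is not. The key secondary OC 0 to 96 h analysis keeps every mITT subject, with zeros for non-users.
- *That mean daily consumption has no all-mITT counterpart.* Only the label is missing. Over a fixed 0 to 96 h window, mean daily MED is total MED divided by 4, so the ANOVA in Table 14.2.4.1.1 gives the same F and p.
- *That time to second rescue has the same fault.* SAP 7.5.5 says "Time to second rescue will also be explored for subjects who receive the first rescue prior to 60 minutes post-dose". That subset is also post-randomisation, but the planned output is Kaplan-Meier curves and, at most, medians with confidence intervals by arm. No log-rank test, hazard ratio or between-arm p-value is specified, so it is already descriptive.

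It is also fair to object that the reversal examples are constructed. They are: with a 50% cut in heavy users' doses, or with no light users, the sign is correct.

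The reply does not rescue the ANOVA. Disclosing the subset does not make its between-arm p-value a test of treatment, and SAP 7.5.4 did not ask for one.

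**Conclusion.** The concern holds for Tables 14.2.4.2.1 and 14.2.4.2.2, as a minor point. Run as titled, their between-arm difference and p-value do not estimate a randomised treatment effect, and their titles go beyond SAP 7.5.4.

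The direction and size of the distortion cannot be fixed from the documents. Under the assumed patterns it ranges from none, through attenuation to 75% of the effect or less, to reversal. A reader should not infer that CA-008 will look harmful in these tables. That depends on how many light users become opioid-free relative to the dose reduction in the remaining users, and the documents give neither. They support only that opioid use is expected to differ by arm. The primary endpoint, the key secondary endpoints and the sample size are untouched.

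**What to change.** Before unblinding:
1. Make Tables 14.2.4.2.1 and 14.2.4.2.2 descriptive by arm (n, mean, SD, median, range), with no ANOVA, p-value or confidence interval for a treatment difference. Retitle them to match SAP 7.5.4.
2. Label the population as a post-randomisation subset, and state what makes a subject a user (opioid or any rescue) and over which window.
3. State in SAP 7.5.4 that inference on opioid consumption rests on the full-mITT analysis with zeros. If the mean daily scale is reported, give it for that population too.

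The cost is SAP and table-shell wording only. No data collection, subjects or confirmatory analysis change, and the clinical description of how much users took is kept.
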